## 6.5 Data Summarization and Presentation

All TRL345 serum concentrations and/or PK parameters descriptive statistics will be generated using SAS® Version 9.4 or higher.

The serum concentrations of TRL345 will be listed and summarized by dose group, treatment and time point for all subjects in the PK Population. Serum concentrations of TRL345 will be presented with the same level of precision as received from the bioanalytical laboratory (i.e., 3 significant figures). Summary statistics, including sample size (n), arithmetic mean (mean), standard deviation (SD), coefficient of variation (CV%), standard error of the mean (SEM), minimum, median, maximum, and range will be calculated for all nominal concentration time points. Excluded subjects or data will be included in the concentration listings but will be excluded from the summary statistics and noted as such in the tables. All BLQ values will be presented as “BLQ” in the concentration listings and tables but will be set to zero or missing as described in [Section 6.4.1](#) for the calculation of summary statistics and footnoted accordingly.

Mean and individual serum TRL345 concentration-time profiles will be presented on linear and semi-log scales. Individual concentration-time profiles will be based on actual sample times, and mean concentration-time profiles will be based on nominal sample times. Linear mean plots will be presented with and without SD. When there are significant (> 3%) time deviations from nominal sample time points, some concentrations may be excluded from the summary statistics and any corresponding summary figures.

TRL345 PK parameters will be listed and summarized by treatment for all subjects in the PK Analysis Population. PK parameters will be reported to 3 significant figures for individual parameters, with the exception of Cmax, (Ceoi, if warranted) and Cmin which will be presented with same level of precision as received from the bioanalytical laboratory and Tmax, which will be presented with 2 decimal places. Summary statistics (n, mean, SD, CV%, SEM, minimum, median, maximum, range, geometric mean (Geom Mean), and geometric CV% (Geom CV%)) will be presented for all PK parameters. Excluded subjects will be listed in the PK parameter tables, but will be excluded from the summary statistics and noted as such in the tables.

The level of precision for each concentration and PK parameter statistic will be presented as follows: minimum/maximum/range in same precision as in bioanalytical data (i.e., 3 significant figures) and/or parameter output, mean/median/Geom Mean in one more level of precision than minimum/maximum/range, SD/SEM in one more level of precision than mean/median/Geom Mean, n will be presented as an integer, and CV%/Geom CV% will be presented to the nearest tenth.

## **6.6 Preliminary Data and Interim Analysis**

Celerion Biometrics will not perform preliminary or interim analyses.

## **7. IMMUNOGENICITY**

### **7.1 Bioanalytical Method**

Blood samples for immunogenicity will be tested using ELISA for antibodies to TRL345 at Celerion, Lincoln, Nebraska.

## **7.2 Immunogenicity Concentrations**

### **Measurements and Collection Schedule**

Blood samples for ADA will be collected and analyzed for all subjects at the following time points:

- Day 1: Baseline
- Days 8 (168 hours post-SOI), 29 (672 hours post-SOI), 43 (1008 hours post-SOI), and 76 (1800 hours post-SOI)

## **7.3 Data Summarization and Presentation**

The ADA presence will be summarized with frequency counts and percentages for the Immunogenicity Population by treatment (pooled placebo, active treatments, active treatment total) at baseline and each post baseline time point. ADA results will be listed for each subject by time point.

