Serum for PK will be collected on Days 1 (0, 1, 2, 4, 6, 12 hours after start of infusion), 2 (24 hours after start of infusion) and 3 (48 hours after start of infusion), and on Days 8, 15, 29, 43 and 76. Additionally, serum samples will be taken on Days 1, 8, 29, 43 and 76 for measurement of anti-TRL345 antibody levels. Samples taken on Days 1, 43, and 76 will be analyzed using an electrochemiluminescence assay. Samples collected on Days 8 and 29 will be held for exploratory analysis, if warranted, based on Day 43 and Day 76 ADA analysis results. The proportion of subjects with detectable anti-TRL345 antibody responses prior to dosing and IP-emergent anti-TRL345 antibodies will be reported.

Additional serum samples will be collected on Days 1 (pre-infusion and 1 hour after start of infusion), 15, 29, 43, and 76 for *ex vivo* PD assessments, which will be conducted at [name] lab as defined in a separate protocol, whereby the dosed participants of the study will remain anonymous.

Additional serum samples will also be obtained on Days 1 (pre-infusion), 3, 8, 15, 29, and 43 for possible additional exploratory analyses that may be necessary to further explore any unexpected safety or tolerability observations.

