**Notes for Generating the Actual Table:**

Presentation of Data:

- The following PK parameters will be presented in the following order and with following units for TRL345 after single 1-hour Intravenous infusion: AUC0-tlast (µg\*hr/mL), AUC0-inf (µg\*hr/mL), AUC%extrap (%), Cmin (µg/mL), Cmax (µg/mL), Ceoi (µg/mL), Tmax (hr), Tmin (hr), Tlast (hr), Kel (1/hr), t½ (hr), CL (L/hr), and Vss (L/Kg).
- N will be presented as an integer (with no decimal);
- Summary statistics will be presented with same precision as defined in post-text shells.

**Table IIST      Summary of Serum TRL345 ADA Detection Following Administration of a Single 1-Hour Intravenous Infusion of TRL345 or Placebo (Immunogenicity Population)**

	Treatment			
ADA Positive	P (N = X)	A (N = X)	B (N = X)	Active Total (N = X)
Baseline	X (XX%)	X (XX%)	X (XX%)	X (XX%)
Day 8	X (XX%)	X (XX%)	X (XX%)	X (XX%)
Day 29	X (XX%)	X (XX%)	X (XX%)	X (XX%)
Day 43	X (XX%)	X (XX%)	X (XX%)	X (XX%)
Day 76	X (XX%)	X (XX%)	X (XX%)	X (XX%)
Overall ADA Positive	X (XX%)	X (XX%)	X (XX%)	X (XX%)
Treatment A: A single 1-hour intravenous infusion of 1 mg/kg TRL345 (Dose Group 1) Treatment B: A single 1-hour intravenous infusion of 10 mg/kg TRL345 (Dose Group 2) Treatment P: A single 1-hour intravenous infusion of matching placebo (Dose Groups 1 and 2) ADA Positive: Subject with a confirmed positive ADA result. Baseline is the last measurement collected prior to start of dosing. Overall indicates the number of subjects who had a positive ADA result at one or more time point. Percentage is relative to the number of subjects (N) dosed ADA = Anti-drug antibody  Source: Table 14.2.3.1 Program: /CAXXXXX/sas prg/stsas/intext/PROGRAMNAME.sas DDMMYYYY HH:MM				

**Table IAES Treatment-Emergent Adverse Event Frequency by Treatment - Number of Subjects Reporting the Event (% of Subjects Dosed) (Safety Population)**

[figure not shown]
	Treatment				
Adverse Event	P (N = X)	A (N = X)	B (N = X)	Active Total (N = X)	Overall (N = X)
Number of Subjects With TEAEs	XX (XX%)	XX (XX%)	XX (XX%)	XX (XX%)	XX (XX%)
Number of Subjects Without TEAEs	XX (XX%)	XX (XX%)	XX (XX%)	XX (XX%)	XX (XX%)
Eye disorders	XX (XX%)	XX (XX%)	XX (XX%)	XX (XX%)	XX (XX%)
Visual blurred	XX (XX%)	XX (XX%)	XX (XX%)	XX (XX%)	XX (XX%)
Gastrointestinal disorders	XX (XX%)	XX (XX%)	XX (XX%)	XX (XX%)	XX (XX%)

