**Notes for Generating the Actual Tables:**

Presentation of Data:

- PK parameters will be presented in the following order and with following units for TRL345 after single 1-hour Intravenous infusion: AUC0-tlast ( $\mu\text{g}\cdot\text{hr}/\text{mL}$ ), AUC0-inf ( $\mu\text{g}\cdot\text{hr}/\text{mL}$ ), AUC%extrap (%), Cmin ( $\mu\text{g}/\text{mL}$ ), Cmax ( $\mu\text{g}/\text{mL}$ ), Ceoi ( $\mu\text{g}/\text{mL}$ ), Tmax (hr), Tmin (hr), Tlast (hr), Kel (1/hr),  $t_{1/2}$  (hr), CL (L/hr), and Vss (L/Kg).
- PK parameters will be reported to 3 significant figures for individual parameters, with the exception of Cmin and Cmax, which will be presented with same level of precision as received from the bioanalytical laboratory, and Tmax, which will be presented with 2 decimal places.
- The level of precision for each parameter statistic will be presented as follows: minimum/maximum/range in same precision as in bioanalytical data (i.e., 3 significant figures) and/or parameter output, mean/median/Geom Mean in one more level of precision than minimum/maximum/range, SD/SEM in one more level of precision than mean/median/Geom Mean, n will be presented as an integer, and CV%/Geom CV% will be presented to one decimal place.

Table ADAD Serum TRL345 ADA Detection Summary Following a Single 1-Hour Intravenous Infusion of TRL345 or Placebo (Immunogenicity Population)

-----Treatment-----				
ADA Result	P (N = X)	A (N = X)	B (N = X)	Active Total (N = X)
-----				
Baseline				
ADA Unevaluable (%)	X (XX%)	X (XX%)	X (XX%)	X (XX%)
ADA Negative (%)	X (XX%)	X (XX%)	X (XX%)	X (XX%)
ADA Positive (%)	X (XX%)	X (XX%)	X (XX%)	X (XX%)
1:X	X (XX%)	X (XX%)	X (XX%)	X (XX%)
1:XX	X (XX%)	X (XX%)	X (XX%)	X (XX%)
1:XXX	X (XX%)	X (XX%)	X (XX%)	X (XX%)
<Days 8, 29 and 43 will be repeated >				
Day 76				
ADA Unevaluable (%)	X (XX%)	X (XX%)	X (XX%)	X (XX%)
ADA Negative (%)	X (XX%)	X (XX%)	X (XX%)	X (XX%)
ADA Positive (%)	X (XX%)	X (XX%)	X (XX%)	X (XX%)
1:X	X (XX%)	X (XX%)	X (XX%)	X (XX%)
1:XX	X (XX%)	X (XX%)	X (XX%)	X (XX%)
1:XXX	X (XX%)	X (XX%)	X (XX%)	X (XX%)
Overall				
ADA Unevaluable (%)	X (XX%)	X (XX%)	X (XX%)	X (XX%)
ADA Negative (%)	X (XX%)	X (XX%)	X (XX%)	X (XX%)
ADA Positive (%)	X (XX%)	X (XX%)	X (XX%)	X (XX%)
-----				

Treatment A: A single 1-hour intravenous infusion of 1 mg/kg TRL345 (Dose Group 1)

Treatment B: A single 1-hour intravenous infusion of 10 mg/kg TRL345 (Dose Group 2)

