Treatment P: A single 1-hour intravenous infusion of matching placebo (Dose Groups 1 and 2)

Baseline is the last measurement collected prior to start of dosing.

Overall indicates the number of subjects who had a ADA positive result at one or more time points.

Percentage is relative to the number of subjects (N) dosed.

ADA = Anti-drug antibody; ADA positive = Subject with a confirmed positive ADA result

Program: /CAXXXXX/sas\_prg/stsas/tab\_PROGRAMNAME.sas DDMMYYYY HH:MM

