**Notes for Generating the Actual Table:**

Programmer Notes:

- ADA time points are as follows:
  - Day 1: Baseline
  - Days 8 (168 hours post-SOI), 29 (672 hours post-SOI), 43 (1008 hours post-SOI), 76 (1800 hours post-SOI)
- Present confirmatory assay results.
- The 'X' in 1:X, 1:XX, and 1:XXX will be replaced with values that will be provided by the PKist. The rows with 'ADA unevaluable (%)', 'ADA negative (%)', and 'ADA positive (%)' represent overall ratios (%), and the 1:X, 1:XX, and 1:XXX (titers) rows are subsets of that overall ratio (%).

Table CAES Treatment-Emergent Adverse Event Frequency by Treatment -  
 Number of Subjects Reporting the Event (% of Subjects Dosed) (Safety Population)

Adverse Event	Treatment			Active Total (N = X)	Overall (N = X)
	P (N = X)	A (N = X)	B (N = X)		
Number of Subjects With TEAEs	X ( X%)	X ( XX%)	X ( XX%)	X ( XX%)	X ( XX%)
Number of Subjects Without TEAEs	XX ( XX%)	XX ( XX%)	XX ( XX%)	XX ( XX%)	XX ( XX%)
Eye disorders	X ( X%)	X ( X%)	X ( X%)	X ( X%)	X ( X%)
Vision blurred	X ( X%)	X ( X%)	X ( X%)	X ( X%)	X ( X%)
Gastrointestinal disorders	X ( X%)	X ( X%)	X ( X%)	X ( X%)	X ( X%)
Dyspepsia	X ( X%)	X ( X%)	X ( X%)	X ( X%)	X ( X%)
Nausea	X ( X%)	X ( X%)	X ( X%)	X ( X%)	X ( X%)
Musculoskeletal and connective tissue disorders	X ( X%)	X ( X%)	X ( X%)	X ( X%)	X ( X%)
Back pain	X ( X%)	X ( X%)	X ( X%)	X ( X%)	X ( X%)
Muscle cramps	X ( X%)	X ( X%)	X ( X%)	X ( X%)	X ( X%)
Musculoskeletal pain	X ( X%)	X ( X%)	X ( X%)	X ( X%)	X ( X%)
Nervous system disorders	X ( X%)	X ( X%)	X ( X%)	X ( X%)	X ( X%)
Headache	X ( X%)	X ( X%)	X ( X%)	X ( X%)	X ( X%)
Reproductive system and breast disorders	X ( X%)	X ( X%)	X ( X%)	X ( X%)	X ( X%)
Vaginal discharge	X ( X%)	X ( X%)	X ( X%)	X ( X%)	X ( X%)
Respiratory, thoracic and mediastinal disorders	X ( X%)	X ( X%)	X ( X%)	X ( X%)	X ( X%)
Epistaxis	X ( X%)	X ( X%)	X ( X%)	X ( X%)	X ( X%)

Treatment A: < >

Treatment B: < >

Treatment P: < >

Although a subject may have had 2 or more adverse events, the subject is counted only once within a category. The same subject may appear in different categories.

Adverse events are classified according to MedDRA Version 26.1.

TEAEs = Treatment-emergent adverse events

Source: ADaM.< >

Program: /CAXXXX/sas\_prg/stsas/tab/programname2022Q1.sas DDMMYYYY HH:MM

Table CAEE Treatment-Emergent Adverse Event Frequency by Treatment -  
 Number of Adverse Events (% of Total Adverse Events) (Safety Population)

Adverse Event	Treatment			Active Total	Overall

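### The ADA tables ignore the TRL345 level in the same serum, so a negative drawn above the assay's drug tolerance may be read as a true negative

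*SAP*

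**What the plan says.** Immunogenicity is a secondary objective. Its endpoint is the incidence of baseline and product-emergent ADA (Protocol 2.2.3, SAP Section 2). On classification and reporting, the SAP gives the following:

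- **Summary.** SAP 7.3: "The ADA presence will be summarized with frequency counts and percentages for the Immunogenicity Population by treatment".
- **Source of status.** The programmer notes to Table ADAD (SAP 11.3) say "Present confirmatory assay results". Its footnote reads "ADA positive = Subject with a confirmed positive ADA result", and in-text Table IIST (SAP 11.1) has the same definition: "ADA Positive: Subject with a confirmed positive ADA result".
- **Third class.** Table ADAD has a row labelled "ADA Unevaluable" at baseline, at each visit and overall. No rule says when a result goes there. Table IIST shows positives only.
- **Denominator.** Both tables carry the footnote "Percentage is relative to the number of subjects (N) dosed".
- **Assay.** SAP 7.1: "Blood samples for immunogenicity will be tested using ELISA for antibodies to TRL345". SAP Sections 2 and 3 and Protocol 2.2.3 also name ELISA. Protocol 3.1 says "Samples taken on Days 1, 43, and 76 will be analyzed using an electrochemiluminescence assay", and the protocol synopsis agrees with that. No drug tolerance is given for either method.
- **Visits.** Protocol 3.1 and SAP Section 3 hold the Day 8 and Day 29 samples for possible exploratory testing. SAP 7.2 and the shells treat Days 8, 29, 43 and 76 as all analysed.
- **Drug levels.** SAP 6.3 schedules a PK sample at every ADA visit.

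**The concern.** Drug in the serum can bind ADA and hide it from the assay. A negative result is therefore informative only when the drug level is at or below the assay's tolerance. The plan collects the measurement needed to judge this at every ADA visit and then does not use it.

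The dose groups are 10-fold apart. If masking occurs, it acts more strongly at 10 mg/kg, and the side-by-side columns could suggest less ADA at the higher dose for no reason but interference. With six active subjects per group, a reassuring zero is easy to obtain.

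Using the Unevaluable row would not repair the rate. With all dosed subjects in the denominator, moving a result from Negative to Unevaluable leaves the positive percentage unchanged. In Table IIST a masked negative and a true negative look the same.

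**Working it through.** The documents state no ADA rate, tolerance or human PK value, so there is no plan figure to reproduce. The nominal hours are consistent: (day − 1) × 24 gives 168, 672, 1008 and 1800 h for Days 8, 29, 43 and 76, as in SAP 6.3 and 7.2.

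**Inputs**
- From the documents: doses of 1 and 10 mg/kg; 6 active subjects per group; rat half-life 46 h and rat Vss 305 mL/kg (Protocol 1.3.2).
- Assumed: human half-life 14–28 days, volume 50–100 mL/kg, drug tolerance 1, 10 or 100 µg/mL.

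**Step 1: residual drug.** C = (dose/V) × 2^(−(day − 1)/t½). At 10 mg/kg, dose/V is 100–200 µg/mL.
- Day 43 (42 days): fraction left is 2^(−42/14) = 0.125 to 2^(−42/28) = 0.354.
- Day 76 (75 days): fraction left is 2^(−75/14) = 0.024 to 2^(−75/28) = 0.156.

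| Dose group | Day 43, µg/mL | Day 76, µg/mL |
|---|---|---|
| 1 mg/kg | 1.25–7.1 | 0.24–3.1 |
| 10 mg/kg | 12.5–71 | 2.4–31 |

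Under linear PK the 10-fold gap holds at every visit. The 10 mg/kg group needs t½ × log2(10), or 46.5–93 days, to fall to the 1 mg/kg level. Days 43 and 76 are 33 days apart.

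**Step 2: compare with tolerance**
- 1 µg/mL: on Day 43 all negatives in both groups are above it. On Day 76 all at 10 mg/kg are above it, and 1 mg/kg is mixed.
- 10 µg/mL: no 1 mg/kg negative is above it on either day. Every 10 mg/kg negative is above it on Day 43, and Day 76 is mixed.
- 100 µg/mL: none is above it on either day.

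**Step 3: sensitivity**
- Rat half-life: 1008/46 = 21.9 half-lives by Day 43. Even from 200 µg/mL this leaves about 0.00005 µg/mL, so no masking.
- Rat Vss with the assumed human half-lives: 10 mg/kg leaves 4.1–11.6 µg/mL on Day 43 and 0.8–5.1 on Day 76. A tolerance of 10 µg/mL then gives a mixed Day 43.
- If Days 8 and 29 are tested, 10 mg/kg leaves 71–168 and 25–100 µg/mL on the Step 1 assumptions, so the problem is larger there.

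**Step 4: effect on a group of six.** If true incidence is p and a share m of positives is masked, the reported rate is p(1 − m).
- p = 0.33, m = 0.5: reported 0.165. P(0 of 6) rises from 0.67^6 = 9% to 0.835^6 = 34%.
- p = 0.20, m = 0.5: reported 0.10. P(0 of 6) rises from 0.8^6 = 26% to 0.9^6 = 53%.

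**Step 5: choice of denominator.** U is the number of negatives drawn above tolerance.

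| Positives, U (of 6) | SAP: positives/6 | Drop U: positives/(6 − U) | Range: positives/6 to (positives + U)/6 |
|---|---|---|---|
| 1, 3 | 17% | 1/3 = 33% | 17%–67% |
| 1, 5 | 17% | 1/1 = 100% | 17%–100% |
| 0, 3 | 0% | 0/3 = 0% | 0%–50% |
| 0, 6 | 0% | 0/0, undefined | 0%–100% |

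**The case against.** A reader might infer that the SAP counts high-drug negatives as Negative and that incidence therefore is understated. The documents do not support this. Table ADAD has a separate Unevaluable row, and no text assigns high-drug negatives to either class. The gap is that the row has no rule. Understatement is a risk whose size depends on human half-life and drug tolerance, neither of which is given, and the tolerance scenarios run from no effect to both groups affected. That limits the claim but does not remove it, because the N-dosed percentage is the same whichever row is used.

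A reader might also take Days 43 and 76 as the only visits tested. The documents conflict on this. Testing the earlier visits would not help, since drug is higher then. Holding them until later results call for it could let masked negatives suppress the trigger.

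Three further objections:
- **ADA is only described, in 12 active subjects, and is not among the listed cross-dose comparisons.** True, and it limits the severity. Appendices 16.2.5.5 and 16.2.5.6 would let a reader match drug level to ADA result by hand, but without a stated tolerance the match cannot be interpreted.
- **Removing only high-drug negatives from the denominator biases the rate upward.** Correct. Step 5 shows 1/6 becoming 1/1, so the remedy must not do this.
- **The Overall row counts positives at any time point, baseline included, so it can overstate product-emergent ADA.** Also correct, so the net direction in that row is not fixed. It is a separate matter and does not offset masking at a given visit.

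**Conclusion.** The point holds as a defect in the classification and denominator rules, not as a demonstrated bias. The plan takes ADA status from the confirmatory result over all dosed subjects, leaves Unevaluable undefined and does not use the same-visit TRL345 level. Negatives drawn above the assay's tolerance may then be read as true negatives. Any masking would lower the ADA-positive count at that visit and, if PK is linear, would fall mainly on 10 mg/kg.

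On the assumed half-life and volume, 10 mg/kg leaves about 12.5–71 µg/mL on Day 43 and 2.4–31 on Day 76. A tolerance of 10 µg/mL would make the whole 10 mg/kg Day 43 row of negatives uninformative and leave 1 mg/kg untouched. A tolerance near 100 µg/mL, or a half-life near 46 h, would leave both visits unaffected. The change should be made, because the data are already collected and the rule reclassifies nobody if drug is low.

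**What to change.** In SAP 7.3 and Tables ADAD and IIST:

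1. Define a confirmed positive as Positive; a negative with same-visit TRL345 at or below the validated drug tolerance as Negative; and a negative above it as Unevaluable. State the tolerance.
2. Replace the N-dosed percentage footnote in both tables; do not add a second denominator beside it. Show Positive, Negative and Unevaluable counts by dose group and visit, and add the Unevaluable row to Table IIST.
3. Report incidence as a range from Positive/N tested (all unevaluable taken as negative) to (Positive + Unevaluable)/N tested. This avoids the inflation from dropping high-drug negatives alone.
4. Name one ADA assay throughout (Protocol synopsis, 2.2.3 and 3.1; SAP Sections 2, 3 and 7.1), because tolerance is assay-specific.
5. State whether Days 8 and 29 are analysed, reconciling Protocol 3.1 and SAP Section 3 with SAP 7.2 and the shells.

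The cost is SAP and protocol wording and one merge of ADA with PK records. No new samples are needed. The downside is a wider and less favourable statement of ADA incidence at 10 mg/kg if drug proves to be above tolerance.

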## **8. SAFETY**

All relevant case report form (CRF) and clinical laboratory data will be listed by subject and chronologically by assessment time point. This will include rechecks, unscheduled, and early termination assessments.

Applicable continuous variables will be summarized using n, mean, SD, minimum, median, maximum, and range. Data from subjects who received the placebo treatment will be pooled across dose groups.

The level of precision will be presented as follows: minimum/maximum/range in the same precision as in the database, mean/median in one more precision level than minimum/maximum/range, SD in one more precision level than mean/median, and n will be presented as an integer. Percentages will be presented as an integer.

Where individual data points are missing because of dropouts or other reasons, the data will be summarized based on reduced denominators.

Baseline will be the result closest and prior to start of dosing unless otherwise stated. Summaries for post-baseline time points will not include rechecks, unscheduled, or early termination measurements.

Tables summarizing safety data by assessment time point will only include summaries for baseline and post-baseline time points.

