5.7 Management of Infusion Reactions

It is required that all sites have the personnel, equipment, and medications to manage hypersensitivity reactions. Subjects must be monitored closely for signs and symptoms of an infusion reaction (IR) (e.g., fever $>38^{\circ}\text{C}$ (100.4°F), chills, flushing, bradycardia, hyper- or hypotension, itching, flushing urticaria, nausea, vomiting, abdominal pain, chest tightness, angioedema, or respiratory distress). In the event of an IR, the infusion should be slowed or stopped and restarted at the discretion of the Investigator. If a severe IR occurs (Grade 3 or 4 signs or symptoms), discontinue infusion and institute treatment as appropriate. Any infusion-related adverse event will be reported to the SMC within 24 hours.

In addition, if a subject experiences a severe IR, the following procedures will be undertaken:

- A targeted physical examination to capture medically relevant details, including but not limited to, a thorough dermatologic examination; a chest examination for breath sounds, stridor or wheezing; and a cardiac examination with attention to irregular heartbeat.
- Vital signs (sitting or supine blood pressure, heart rate, and body temperature) will be captured at the time of the IR and at least every 15 minutes until the resolution or stabilization of the IR. In addition, hematology and serum chemistry will be taken.

The Investigator may administer any medically indicated pharmacologic agent or procedure intended to relieve symptoms. Signs and symptoms of the IR and drugs given for treatment are to be recorded in the medical record and in the separate electronic case report form (eCRF) page for possible and probable IRs.

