Descriptive statistics will be presented for the by-subject averages of each ECG parameter by assessment time point and treatment (pooled placebo and active treatment). Change from baseline will be summarized in a similar manner. Baseline is defined as the average of the valid ECG set closest and prior to start of dosing which may include unscheduled assessments. This will typically be the average of the triplicate ECG set collected at Screening. At postdose time points, the average of the first valid ECG set will be used in the analysis. Postdose unscheduled and early termination measurements will not be included in summaries.

All ECG data will be listed by-subject and QTc values > 450 msec will be flagged. A separate by-subject listing will be provided to display the ECG average values to be used during analysis where QTc average values > 450 msec and increase from baseline > 30 msec will be flagged.

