“There were no events that met this criteria.”

Source: ADaM.< >

Program: /CAXXXXX/sas\_prg/stsas/tab/programname2022Q1.sas DDMMYYYY HH:MM

Table CLBO Out-of-Range Values and Recheck Results - <Clinical Laboratory Panel> (Safety Population)

Dose Group	Subject Number	Age/ Sex	Study Period	Treatment	Day	Hour	Date	Time	Parameter1 <Range> (Unit)	Parameter2 <Range> (Unit)	Parameter3 <Range> (Unit)	Parameter4 <Range> (Unit)
1	0001	XX/X	Screen				DDMMYYYY	HH:MM:SS	XX H		XX L	XX H
			1	A	-X	-X.XX	DDMMYYYY	HH:MM:SS	XX L	XX L		XX L

Programmer Note: Replace Parameter1, 2 etc. with actual lab tests in the study. Sort unscheduled assessment and early termination chronologically with other scheduled assessments and rechecks. Recheck should be sorted with the scheduled time point the recheck is for. Unscheduled and Early Termination records should only be included if they are out of range or recheck results.

Treatment A: < >  
 Treatment B: < >  
 Treatment P: < >  
 F = Female; M = Male  
 H = Above reference range; L = Below reference range

Source: < >  
 Program: /CAXXXXX/sas\_prg/stsas/tab/programname2022Q1.sas DDMMYYYY HH:MM

Table CLBD Clinical Laboratory Summary and Change From Baseline - <Clinical Laboratory Panel> (Safety Population)

Laboratory Test (units)	Reference Range	Time Point	Statistic	Treatment			Change From Baseline		
				P (N = X)	A (N = X)	B (N = X)	P	A	B
Testname (unit)	< - >#	Baseline	n	X	X	X			
			Mean	X.X*	X.X	X.X			
			SD	X.XX	X.XX	X.XX			
			Minimum	XX	XX	XX			
			Median	X.X	X.X	X.X			
			Maximum	XX	XX	XX			
			Range	XX	XX	XX			
		Day 2	n	X	X	X	X	X	X
			Mean	X.X	X.X^	X.X	X.X	X.X	X.X
			SD	X.XX	X.XX	X.XX	X.XX	X.XX	X.XX
			Minimum	XX	XX	XX	XX	XX	XX
			Median	X.X	X.X	X.X	X.X	X.X	X.X
			Maximum	XX	XX	XX	XX	XX	XX
			Range	XX	XX	XX	XX	XX	XX

Programmer Note: Treatment means at specific time points will be flagged (with a \* or ^) if they are above or below the reference range. This only applies to the clinical laboratory treatment results (i.e., not the change from baseline or any other endpoints). Time Point column will match those found in the Clinical Laboratory Tests section of the SAP.

Treatment A: < >

Treatment B: < >

Treatment P: < >

Baseline is the last measurement collected prior to start of dosing.

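### Unscheduled and early-termination lab and vital-sign values enter no by-treatment lab or vital-sign table, an undeclared departure from Protocol 8.2

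*SAP*

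**What the plan says.** **The exclusion.** SAP Section 8 sets the general rule for safety tables: "Summaries for post-baseline time points will not include rechecks, unscheduled, or early termination measurements". SAP 8.7 has a matching rule for ECGs: "Postdose unscheduled and early termination measurements will not be included in summaries".

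**What is kept.** The same section commits to listing all case report form and laboratory data by subject, and adds: "This will include rechecks, unscheduled, and early termination assessments". The programmer note to shell CLBO (SAP 11.3), which serves the out-of-range laboratory tables, reads: "Unscheduled and Early Termination records should only be included if they are out of range or recheck results". The exclusion does not reach baseline: "Baseline will be the result closest and prior to start of dosing unless otherwise stated". For ECGs, SAP 8.7 expressly lets an unscheduled pre-dose record serve as baseline.

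**What the protocol requires to be collected.** In a severe infusion reaction, Protocol 5.7 says vital signs "will be captured at the time of the IR and at least every 15 minutes until the resolution or stabilization of the IR". It continues: "In addition, hematology and serum chemistry will be taken". Protocol 6.4.5 applies the Day 43 assessments, including chemistry, hematology and vital signs, to a subject who terminates early.

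**What the protocol promises.** Protocol 8.2 says that all safety data will go into both listings and summaries. The primary endpoint (Protocol 2.2.1, SAP Section 2) covers the incidence and severity of abnormal chemistry, hematology and vital signs, named separately from adverse events.

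**The concern.** An incidence endpoint asks whether a subject was abnormal at any time after dosing. The planned laboratory and vital-sign tables answer a narrower question: what was seen at the scheduled visits. Values outside the schedule often exist because something happened, such as a severe reaction, follow-up of an adverse event, or a withdrawal. If they are left out and no any-time row replaces them, the treatment columns for the primary endpoint can omit the values a reader of a first-in-human study most wants to compare between 1 mg/kg, 10 mg/kg and placebo.

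The departure is also undeclared. SAP Section 9 lists several protocol-planned safety summaries that will not be produced, among them laboratory abnormalities by severity and adverse events by time from dosing. It does not say that by-visit tables will use scheduled values only.

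**Working it through.** The plan states no figure to reproduce, so the check traces each kind of record to the tables it can reach.

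**Scheduled slots.** SAP 8.5 summarizes laboratory tests at baseline (Day -1) and then on Days 2, 3, 8, 15, 29 and 43. Protocol 6.4.1 likewise places all Day 1 laboratory draws before dosing. A laboratory sample taken during a reaction on Day 1 therefore has no scheduled slot. SAP 8.6 summarizes vital signs on Day 1 at 0.25, 0.5, 1, 2 and 5 hours from the start of infusion, then on the same days as the laboratory tests.

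**Tracing the records.**

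| Post-dose record | By-visit table (14.3.5.1, .3, .5) | Shift table (14.3.5.2, .4) | Out-of-range table (14.3.4.1, .2) | Listing | AE tables |
|---|---|---|---|---|---|
| Reaction chemistry and hematology | No | No | If out of range | Yes | Reaction itself; a result if judged clinically significant |
| Extra reaction vital signs | No | None planned | None planned | Yes | Through the reaction |
| Scheduled vital signs falling in a reaction | Yes | None planned | None planned | Yes | Through the reaction |
| Early-termination chemistry and hematology | No | No | If out of range | Yes | If judged clinically significant |
| Early-termination vital signs | No | None planned | None planned | Yes | If reported as an AE |

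Tables 14.3.4.1 and 14.3.4.2 show individual values with the treatment beside them, but no counts by treatment. No laboratory, vital-sign or ECG shell has a worst-post-dose or any-time row.

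**Scale, under assumptions.** The documents give no rate of severe infusion reactions. With assumed rate p per active subject, the chance of at least one among n subjects is 1 − (1 − p)^n.

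| Assumed p | n = 6 (one dose group) | n = 12 (both) |
|---|---|---|
| 1% | 5.9% | 11.4% |
| 2% | 11.4% | 21.5% |
| 5% | 26.5% | 46.0% |
| 10% | 46.9% | 71.8% |

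The range is wide, so the table shows only that the situation need not be rare.

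**One assumed reaction.** Suppose it starts 20 minutes into the infusion and lasts 2 hours. Monitoring every 15 minutes gives 120/15 + 1 = 9 sets of vital signs. Three scheduled times (0.5, 1 and 2 hours) fall in that period and would be summarized. The reaction's chemistry and hematology would contribute no value to the descriptive or shift tables.

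**One assumed withdrawal.** Suppose one of 6 active subjects leaves after Day 8, with normal scheduled results and an abnormal early-termination panel. Any-time incidence is 1/6 = 16.7%. Among the 5 who remain, the scheduled visits from Day 15 could show 0/5 = 0%.

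**The case against.** The case for leaving the plan alone is substantial.

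- **Nothing is lost from the report.** Every value is listed, and listings for 16 subjects can be read in full. This stands, and it is why the point is a reporting gap and not a loss of data.
- **The safety signal arrives by other routes.** A severe reaction is coded as an adverse event and reaches the treatment-emergent tables with its grade. So does any laboratory abnormality judged clinically significant. This stands in part. Under Protocol 7.3 a laboratory result becomes an event only after a confirming repeat and the investigator's judgement, and the infusion-reaction flag appears only in the adverse-event listing.
- **Scheduled-only by-visit tables are a legitimate choice.** Irregularly timed values would make by-visit means harder to interpret. This stands, and those tables should not change.
- **Protocol 8.2 may speak of types of data, not every value.** That reading is possible. On it, a line in SAP Section 9 costs nothing; on the literal reading, the line is needed.
- **The synopsis folds laboratory and vital-sign findings into adverse-event incidence.** It does, but Protocol 2.2.1 and SAP Section 2 name them separately.

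A reader might also infer that the summaries systematically discard the worst values and bias the safety result towards no effect. The documents do not support that. The rule is post-baseline only. Scheduled Day 1 vital signs taken during a reaction are summarized. Excluding rechecks keeps the first, possibly abnormal, result in the table. Early termination is not shown to depend on safety: Protocol 4.3.2 lists non-safety reasons, although investigator discretion could cover an adverse event. The analysis is descriptive, without formal testing.

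**Conclusion.** The point holds as a limited gap that should be closed. Laboratory tests and extra vital signs from a severe reaction, and early-termination values, enter no by-treatment laboratory or vital-sign summary, and no any-time row stands in for them. The incidence endpoint is therefore incompletely tabulated, and SAP Section 9 does not declare the departure from Protocol 8.2. The gap is clearest for vital signs, which have neither a shift table nor an out-of-range table.

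The size cannot be stated. The comparison of 1/6 with 0/5 is a constructed case: it assumes that the only abnormal values occur at early termination. The shift shell prints counts without percentages, and a withdrawn subject may be replaced (Protocol 4.3.3). It should not be read as an estimate.

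A reader might extend the point to ECGs because of SAP 8.7. Neither Protocol 5.7 nor 6.4.5 requires an ECG, so no ECG mandated by those sections is excluded, and all ECGs are listed with high QTc values flagged.

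**What to change.** 1. Keep the by-visit tables as they are.
2. Add worst-post-dose rows to shift Tables 14.3.5.2 and 14.3.5.4, giving each subject's lowest and highest category at any time after dosing against the baseline category.
3. Add rows to vital-sign Table 14.3.5.5 that summarize each subject's post-dose minimum and maximum by treatment.
4. Build these rows from all valid post-dose records: scheduled, unscheduled and early termination.
5. State in SAP Section 9 that by-visit tables use scheduled values only.

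Early-termination values should not be moved into the nearest visit window, since that would alter the by-visit tables. A similar ECG row is optional.

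The cost is SAP wording and a little programming: derived worst-value records for each test, with no new data collection. One drawback needs a footnote: a worst value depends partly on how often a subject was measured, so a subject monitored every 15 minutes has more chances to show an extreme than one seen only on schedule.
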